1.0 Study Summary

Study Title	Phonation therapy to improve symptoms and lung physiology in patients referred for pulmonary rehabilitation.
Study Design	Randomized Controlled Trial
Primary Objective	1) Improvement in patient symptoms (Borg dyspnea score)
Secondary Objective(s)	1) Improvement in time of breath hold. 2) Improvement in lung physiology – FVC, FEV1, NIF 3) Improvement in quality of life
Research Intervention(s)/ Investigational Agent(s)	1) Tonation Breathing Techniques (TBT) Exercises 2) Music Driven Vocal Exercises (MDVE)
IND/IDE #	
Study Population	Patients who are referred to Pulmonary Rehabilitation for symptomatic chronic lung disease
Sample Size	16
Study Duration for individual participants	8-weeks
Study Specific Abbreviations/ Definitions	FVC – forced vital capacity; FEV1 – forced expiratory volume in 1 second; NIF – negative inspiratory force; PR- Pulmonary Rehabilitation; TBT – Tonation Breathing Techniques; MDVE – Music Driven Vocal Exercises; PFT – pulmonary function testing

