2.0 Objectives*

The objective of this study is to determine whether breathing and vocalization exercises improve dyspnea in patients who are referred for pulmonary rehabilitation (PR).

The specific aims are to determine the following:

- 1) Do breathing and vocalization exercises improve subjective pulmonary symptoms and objective pulmonary function in patients referred for PR, compared to no intervention?
 - a. Specific outcomes include: subjective: Borg dyspnea score
 - b. Specific outcomes include: objective: Forced expiratory volume in 1 second (FEV1), forced vital capacity (FVC), Peak Flow, Negative Inspiratory Force (NIF), peak flow
- 2) Do breathing and vocalization exercises improve subjective pulmonary symptoms and objective pulmonary function, compared to calm normal breathing?
 - a. Specific outcomes include: subjective: Borg dyspnea score
 - b. Specific outcomes include: objective: FEV1, FVC, NIF, peak flow
- 3) Is there a difference between two different proposed techniques of breathing and vocalization exercise techniques to improve subjective pulmonary symptoms and objective pulmonary function?
 - a. Specific outcomes include: subjective: Borg dyspnea score
 - b. Specific outcomes include: objective: FEV1, FVC, NIF, peak flow

Our hypotheses are that breathing and vocalization techniques are a) feasible; b) can improve subjective and objective pulmonary outcomes; c) there is no significant difference between the two proposed techniques of breathing and vocalization techniques.

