4.0 Study Endpoints*

- 1) Specific outcomes include: subjective: Borg dyspnea score
- 2) Specific outcomes include: objective: FEV1, FVC, NIF, peak flows (all obtained from spirometry)

No specific safety outcomes are proposed, as no significant risks are associated with the proposed intervention.

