17.0 Data Management* and Confidentiality

Descriptive analyses will be performed first on each of 4 categories. Chi-squared tests and ANOVA testing will be performed, although with low sample size, significance is not expected in these analyses. No power analysis will be performed, as this will be a pilot study.

Baseline data, including patient demographics, baseline pulmonary function test results, baseline Borg dyspnea score will be saved into a REDCap database. This database will only be accessible by study investigators. De-identified database will be downloaded for analysis, and this will be stored on the PI's G: drive research folder. Study records will be stored according to the MHS Record Retention Policy VII-4, which is minimum 4 years after study completion.

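### The primary objective is worded only as improvement in Borg score and no comparison is designated primary, although the crossover provides a within-patient contrast that would isolate the technique.

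*Protocol*

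**What the plan says.** The primary objective in section 1.0 reads "Improvement in patient symptoms (Borg dyspnea score"). That line names an outcome and a direction, but no comparator, time point or effect measure.

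Section 2.0 opens in the same way: "The objective of this study is to determine whether breathing and vocalization exercises improve dyspnea in patients who are referred for pulmonary rehabilitation (PR"). It then lists three aims, each with its own comparison:

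- Aim 1: "objective pulmonary function in patients referred for PR, compared to no intervention".
- Aim 2: "objective pulmonary function, compared to calm normal breathing".
- Aim 3: "Is there a difference between two different proposed techniques of breathing and vocalization exercise techniques".

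All three carry the same outcomes: Borg, FEV1, FVC, NIF and peak flow. Hypothesis (b) is that the techniques "can improve subjective and objective pulmonary outcomes". Section 4.0 lists Borg and then the lung-function measures without marking any as primary.

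Section 6.0 sets out four sequences of 4 participants each: normal breathing then TBT, TBT then normal breathing, and the same two orders for MDVE. (The technique in the second period of arm 2a is printed with an undefined abbreviation, WT. It stands under the MDVE heading and is read here as MDVE.) All participants attend the 8-week rehabilitation programme. Borg is collected at baseline, week 4 and week 8.

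Section 17.0 plans descriptive analyses of four categories, then: "Chi-squared tests and ANOVA testing will be performed, although with low sample size, significance is not expected in these analyses". The tests are not tied to an outcome or a contrast.

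**The concern.** A reader cannot tell from the protocol which comparison answers the primary question. The candidates are the change from start to end of rehabilitation, technique against normal breathing (pooled or by technique), and one technique against the other. They estimate different things, and only technique against normal breathing bears on whether a technique relieves dyspnea.

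The gap matters in this design because rehabilitation runs throughout. Improvement, taken by itself, is satisfied by a gain that rehabilitation could produce alone. The comparator in aim 1 might have settled the matter, but no arm and no period goes without a session, so that comparison cannot be made as written. The analysis named in section 17.0, if it compares the four sequence groups, sets aside what the crossover was built to give: each participant as his or her own control. With 16 participants that loss is large.

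**Working it through.** **1. The plan's own figure.** 4 arms × 4 participants = 16, as stated in section 6.0. There is no power calculation to reproduce, since the protocol gives no alpha, effect size or SD.

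**2. What each comparison estimates.** Let r4 and r8 be the rehabilitation gains by weeks 4 and 8, τ the technique effect, and λ any technique effect that persists into a following normal-breathing period.

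| Sequence | Week 4 | Week 8 |
|---|---|---|
| Normal breathing, then technique | r4 | r8 + τ |
| Technique, then normal breathing | r4 + τ | r8 + λ |

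- Baseline to week 8, all participants: r8 + (τ + λ)/2. Rehabilitation and technique are mixed.
- Week 8 minus week 4, half the difference between the two orders: [(r8 − r4 + τ) − (r8 − r4 − τ + λ)]/2 = τ − λ/2. Rehabilitation cancels. Carryover remains, at half weight.
- Week 4, technique-first against normal-first: (r4 + τ) − r4 = τ. This is free of carryover, but between patients.

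**3. Precision.** Assumptions, none from the protocol: τ = 1 SD, equal for both techniques; within-patient correlation 0.5; λ = 0; two-sided 0.05; 4 per sequence.

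- *Within-patient, pooled, period-adjusted.* SD of the week-8 minus week-4 difference = √[2(1 − 0.5)] = 1. Standard error of the effect = 1/√16 = 0.25. Noncentrality = 1/0.25 = 4 on 16 − 4 = 12 df. Power = 0.956.
- *Four-group ANOVA at week 8.* Two groups are on a technique and two on normal breathing, so each group mean lies 0.5 SD from the overall mean. Noncentrality = 4 × 4 × 0.5² = 4 on 3 and 12 df. Power = 0.27.
- *Week-4 comparison, 8 against 8.* Standard error = √(2/8) = 0.5. Noncentrality = 1/0.5 = 2 on 14 df. Power = 0.46. This suits a sensitivity result better than a primary one.

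A simulation of 20,000 trials gives 0.96 and 0.27 for the first two.

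**4. False positives.** Null crossover trials were simulated at an assumed two-sided 0.05.

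- At least one of three Borg contrasts (TBT v normal, MDVE v normal, TBT v MDVE) is significant in 0.11 to 0.12 of trials. The value under independence would be 1 − 0.95³ = 0.14.
- A significant result favouring either technique over normal breathing, on any of five outcomes (10 tests), occurs in 0.14 of trials at between-outcome correlation 0.8 and 0.22 at correlation 0. Check at independence: 1 − 0.975¹⁰ = 0.22.
- The same for Borg alone: 1 − 0.975² = 0.05.

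**The case against.** Several points on the other side stand. The protocol does name comparators, in sections 2.0 and 6.0; what is missing is the designation of one as primary. Section 1.0 already makes Borg the only primary outcome, so outcomes are unranked only in sections 2.0 and 4.0. The study is plainly a pilot, and sections 8.0 and 17.0 say significance is not expected. Alpha and the test hierarchy may be set in a statistical analysis plan that was not available here, so their absence is no finding.

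Two stronger readings are tempting, and the documents support neither.

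- A reader might infer that rehabilitation alone would be reported as a significant technique effect. No baseline-to-week-8 test is stated anywhere, and a gain shared by all four arms cannot by itself make an ANOVA across arms significant. Any probability for this event would rest on assumed rehabilitation effects and on a test the protocol does not contain.
- A reader might count three aims × five outcomes = 15 tests and quote a false-positive rate of about 0.40. That value reproduces at between-outcome correlation 0.5, but for TBT v normal, MDVE v normal and TBT v MDVE, not for the three aims. It counts results in either direction and includes TBT v MDVE, where hypothesis (c) expects no difference. The protocol does not commit to 15 tests.

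It is also fair to say that section 17.0 does not exclude a repeated-measures ANOVA with period terms, which would use the within-patient data. The four categories make a comparison of arms the natural reading, and the text should settle it. None of this supplies the missing primary contrast. Which question the primary objective asks belongs in the protocol, and being a pilot does not remove the need to state it.

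**Conclusion.** The point holds as a defect in the definition of the primary objective. No contrast is designated primary, one of the three named comparators does not exist in the design, and neither before-after change nor a comparison of the four sequence groups isolates the technique efficiently. Under the assumptions given (1 SD effect in both techniques, within-patient correlation 0.5, no carryover, two-sided 0.05), the choice of contrast moves power from 0.27 to about 0.95 with the same 16 participants. The size of that gap depends on the assumed effect and correlation. That baseline-to-week-8 change mixes rehabilitation with technique does not depend on them.

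The within-patient contrast has one real weakness. Section 6.0 describes no washout, so a lasting benefit of a technique learned first would pull the estimate towards zero by half its size.

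Multiplicity is secondary: about 0.12 for any of three Borg contrasts, and 0.14 to 0.22 for a false result favouring a technique across five outcomes.

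**What to change.** - **Sections 1.0 and 17.0:** define the primary contrast as the within-patient difference in Borg score between the technique and normal-breathing periods, techniques pooled, using the week-4 and week-8 scores and adjusted for period.
- **Section 17.0:** state that carryover cannot be excluded because no washout is described, and show the week-4 comparison between technique-first and normal-first groups as a sensitivity result.
- **Section 17.0:** state that baseline-to-week-8 change is descriptive and is not evidence for a technique.
- **Section 2.0:** reword or remove the no-intervention comparison in aim 1.
- **Sections 2.0, 4.0 and 17.0:** label the single-technique comparisons, TBT v MDVE and all lung-function results as exploratory, reported as estimates with 95% confidence intervals.

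This needs a few lines of text and no new participants, visits or measurements. The price is that an isolated p < 0.05 on a secondary outcome or a single technique could no longer be presented as a finding.

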Pulmonary function testing is standard for all patients who receive PR – testing before and after PR is routine clinical course. We propose an additional PFT study at 4 weeks, as part of the research protocol (covered by the Department of Medicine funding)

In summary, the interventions for research purposes will include:

- 1) 20-minute sessions after PR for intervention (TBT or MDVE) or normal breathing for twice a week for the 8 weeks they are participating in PR.
- 2) PFT at end of week 4

Proposed subjective outcomes are routinely asked of PR patients, but will be collected at baseline, at 4 weeks (mid-way), and at 8 weeks (end) of PR.

Proposed objective outcomes:

- 1) For FEV1, FVC – these are routinely collected at baseline and at end of PR. We propose an additional PFT study at 4 weeks, covered by the DOM Faculty Development Fund.
- 2) For peak flow and NIF – these are procedures that ask for patient to breathe maximally for inspiration and expiration. They are not routine measures collected but are routine bedside measurements for pulmonary patients that can be collected for any person without any additional risk or cost.

Data will be obtained as following:

- 1) Routinely obtained information will be collected from EPIC into a REDCap database. This includes:
 - a. Patient demographics – name, MRN, DOB, sex, gender, race, ethnicity, height, weight, BMI,
 - b. Pulmonary history: reason for PR referral (routine collection); date of symptom onset; date of diagnosis of lung pathology; prior PFT findings – FEV1, FVC, peak flow, NIF.
 - c. PR questionnaire info: Borg dyspnea score at baseline and each visit (routine collection)

There are no plans for long-term follow-up.

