9.0 Study Timelines*

An individual participants time in the study will be approximately 8 weeks.

Time 0 – Informed Consent signed.

Weeks 1-8 – normal Pulmonary Rehabilitation 3 times a week, with phonation intervention (TBT or MDVE) or silent breathing time.

On last session of week 4 and week 8: PFT's, NIF, VC, peak flows will be measured. Borg dyspnea scale will be collected.

We hope to collect 16 participants for this study by November 2022, and have primary analysis completed by December 2022 for submission to American Thoracic Society 2023 presentation.

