13.0 Recruitment Methods

Patients who are scheduled to start Pulmonary Rehabilitation will be called by one of the consenting investigators. The study will be described and any questions will be answered. The consent form will be sent to the patient to review in full. On the first day of Pulmonary Rehabilitation (PR), the patient will meet with a study investigator in a private room, and any further questions will be answered, and if patient is agreeable, will sign the consent form.

Source of participants will be all referred for Pulmonary Rehabilitation (patients are within the practice of the PI).

We will request partial HIPAA waiver to access patients' charts who are scheduled for Pulmonary Rehabilitation and assess inclusion and exclusion criteria and study eligibility. This will allow us to call patients and talk to them about their participation in this study, and answer questions prior to obtaining full informed consent.

A payment of \$10 by MetroHealth gift card will be given to the patient upon completion of 4 weeks of the research study / PR. An additional \$20 will be added to the participant's MetroHealth gift card on the last day of PR after completion of the study surveys and testing. This will be funded through the Pulmonary/CC Fellow MH Foundation fund.

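### Breath-hold time and quality of life are secondary objectives that the protocol never measures, and the source of a pre-treatment NIF is unreconciled

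*Protocol*

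**What the plan says.** Section 1.0 gives three secondary objectives: "Improvement in time of breath hold", lung physiology (FVC, FEV1 and NIF), and "Improvement in quality of life".

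Sections 2.0 and 4.0 name one subjective outcome, the Borg score, and four objective ones: FEV1, FVC, NIF and peak flow. Section 4.0 adds that all four come from spirometry. In Section 6.0 the summary beginning "the interventions for research purposes will include" holds two items, the study sessions and the week-4 PFT. The questionnaire data in Sections 6.0 and 7.0 are the Borg score alone. Section 13.0 ties the second payment to the participant's final visit: "on the last day of PR after completion of the study surveys and testing".

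On timing, Section 6.0 collects the subjective outcomes at baseline, week 4 and week 8. It says of FEV1 and FVC that "these are routinely collected at baseline and at end of PR", and adds a week-4 test. Of peak flow and NIF it says "They are not routine measures collected but are routine bedside measurements for pulmonary patients", and gives no time point. Among the routinely obtained chart data, Sections 6.0 and 7.0 both list "prior PFT findings – FEV1, FVC, peak flow, NIF". Section 9.0 states for the last session of weeks 4 and 8 that "NIF, VC, peak flows will be measured". Its Time 0 entry is consent only.

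**The concern.** An objective worded as an improvement needs a defined measure, taken before treatment and again afterwards. Breath-hold time and quality of life have no measure, instrument or time point. This is not a detail that a statistical analysis plan could supply, because such a plan analyses collected data and cannot create a measurement that no section schedules.

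For NIF the measure exists, but its pre-treatment value rests on statements that disagree. In the two technique-first arms, the first dated NIF falls at the end of the technique period. If the chart holds no earlier value, no later analysis can recover it. The pilot is meant to supply preliminary data for a larger study, so a gap of this kind bears on its purpose.

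**Working it through.** The protocol gives no figure to reproduce. The check is a cross-reading of each outcome against the sections that would have to measure it.

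| Outcome | Pre-treatment | Week 4 | Week 8 |
|---|---|---|---|
| Borg | yes (6.0) | yes | yes |
| FEV1, FVC | yes, routine (6.0) | yes, research PFT | yes |
| NIF | chart value only, if present | yes (9.0) | yes (9.0) |
| Peak flow | chart value, plausibly with the routine PFT | yes (9.0) | yes (9.0) |
| Breath-hold time | none | none | none |
| Quality of life | none | none | unnamed surveys only (13.0) |

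**Unmeasured objectives.** Breath-hold time occurs once in the protocol, in Section 1.0. Quality of life occurs elsewhere only in Section 3.0, as a result of a cited study. Two of three secondary objectives therefore have no data behind them.

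**Where a pre-treatment NIF could come from.**
- Section 6.0 calls NIF non-routine, while Sections 6.0 and 7.0 extract it as routine chart data.
- Section 4.0 places it within spirometry, while Section 6.0 treats it as a bedside measure.
- Section 10.0 requires a baseline PFT on record and Section 17.0 stores the baseline PFT results. Neither says that NIF must be part of that test.

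**Who is exposed.** Planned allocation (6.0): 4 arms × 4 = 16. Technique-first arms: 2 × 4 = 8. The other 8 have a week-4 NIF before their technique starts.

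**How much technique precedes the first dated NIF.** At two sessions a week (6.0, and the staffing sum in 25.0), 2 × 4 = 8 sessions, or 7 if the test comes before the last session. Section 9.0 can be read as three sessions a week, which gives 3 × 4 = 12, or 11. On either reading almost all of the technique period has passed.

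**How many lack a value.** Let p be the share of charts that hold a NIF, which the protocol does not give. The number of technique-first participants without a pre-technique NIF is 8 × (1 − p). With assumed p = 0, 0.5 and 1, this is 8, 4 and 0. These values span the full range and are not an estimate.

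**The case against.** The strongest reply concerns NIF. Section 9.0 lists no baseline for any outcome, including Borg and FEV1/FVC, for which Section 6.0 does give one. Its silence on NIF is therefore weak evidence that none will be taken. A route is also written down: only patients with earlier PFTs are approached, NIF is among the chart items, and baseline PFT results are stored. This stands. A reader might infer that no baseline NIF is foreseen at all, and the documents do not support that. What they show is an intended source that conflicts with the statement that NIF is not routine and that nothing obliges the chart to contain.

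A reader might also put peak flow on the same footing. That goes too far, because peak flow may be reported with routine spirometry. It is a lesser concern and carries none of the size given here.

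It can further be said that the end-of-study surveys cover quality of life. They appear only in payment text, with no instrument and no baseline, so they cannot support a claim of improvement. Breath-hold time has not even that.

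Finally, this is a pilot without a power analysis, in which significance is not expected. That limits the consequence, but it does not supply missing measurements.

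**Conclusion.** Followed as written, the protocol cannot assess breath-hold time or quality of life. This is the main point, and it rests on no assumption beyond the text.

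The NIF point is narrower: the pre-treatment source is unreconciled and not secured. Technique-first participants without a chart NIF lose the change over the technique period and the baseline adjustment. They number between 0 and 8 of the 8 planned. That 8 assumes 4 per arm, which a random number generator does not by itself guarantee.

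It would be wrong to conclude that NIF becomes unusable or that the primary result is at risk. The within-participant week-4 versus week-8 contrast and the week-4 between-arm contrast (without baseline adjustment where the chart value is missing) both remain. Borg has baseline, week-4 and week-8 values. The inconsistencies should be corrected, but they do not undermine the trial's main comparison.

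**What to change.** (a) Delete breath-hold time and quality of life from Section 1.0. Alternatively, keep them and enter a timed breath hold and one named questionnaire in Sections 4.0, 6.0 and 9.0 at baseline, week 4 and week 8. Week 4 is needed because without it the technique and normal-breathing periods of this crossover cannot be separated.

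(b) Schedule a bedside NIF at the introductory PR session, before the first study session, in Sections 6.0 and 9.0. Include peak flow if the baseline PFT does not report it. Reconcile Sections 4.0 and 6.0 on whether these measures come from spirometry or bedside testing, and on whether they are routine.

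Cost: deletion is free. Keeping both objectives adds 3 × 16 = 48 breath holds and 48 questionnaires for 16 completers. The baseline NIF adds one bedside test per enrolled participant to the 16 × 2 = 32 already scheduled. That is about 16, plus one for each replacement, since Section 14.0 does not count withdrawn participants toward enrolment. Section 6.0 says that the measurement adds neither risk nor cost, and the visit is already held for consent.

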2.0 Objectives*

The objective of this study is to determine whether breathing and vocalization exercises improve dyspnea in patients who are referred for pulmonary rehabilitation (PR).

The specific aims are to determine the following:

- 1) Do breathing and vocalization exercises improve subjective pulmonary symptoms and objective pulmonary function in patients referred for PR, compared to no intervention?
 - a. Specific outcomes include: subjective: Borg dyspnea score
 - b. Specific outcomes include: objective: Forced expiratory volume in 1 second (FEV1), forced vital capacity (FVC), Peak Flow, Negative Inspiratory Force (NIF), peak flow
- 2) Do breathing and vocalization exercises improve subjective pulmonary symptoms and objective pulmonary function, compared to calm normal breathing?
 - a. Specific outcomes include: subjective: Borg dyspnea score
 - b. Specific outcomes include: objective: FEV1, FVC, NIF, peak flow
- 3) Is there a difference between two different proposed techniques of breathing and vocalization exercise techniques to improve subjective pulmonary symptoms and objective pulmonary function?
 - a. Specific outcomes include: subjective: Borg dyspnea score
 - b. Specific outcomes include: objective: FEV1, FVC, NIF, peak flow

Our hypotheses are that breathing and vocalization techniques are a) feasible; b) can improve subjective and objective pulmonary outcomes; c) there is no significant difference between the two proposed techniques of breathing and vocalization techniques.

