6.0 Procedures Involved*

Patients who are referred for pulmonary rehabilitation for chronic lung disease and/or post-COVID19 therapy, who have had pulmonary function testing already will be approached. Pulmonary rehabilitation is an 8-week program (meeting 3 times per week for the 8 weeks). Pulmonary rehabilitation (PR) is standard of care for patients with chronic lung diseases and or post-COVID-19 therapy. Eligible study participants will be called prior to their introductory PR session to explain the research project, and those who are interested will be given full information and offer time to ask questions. We find this necessary for logistics, given many of our patients rely on scheduled transportation to/from PR and this will allow those who are interested in obtaining more information and to consent to the study to arrange for appropriate transportation. Informed consent will be done in person on an individual basis at their introductory PR session, with 1:1 discussion with the study staff and the patient.

As this is a pilot study to determine feasibility, and preliminary data (as no data are currently available for this patient population), we propose 16 participants in total, 4 in each arm of the study. Randomization will occur by random number generator (1-4 for each arm proposed).

Once informed consent is obtained, patients will be randomized to 4 arms of the study. Randomization will be performed using a random number generator.

- 1) Comparing TBT to normal breathing:
 - a. Of the 8 weeks of PR, first 4 weeks will be sessions of normal breathing exercises for 20 minutes, then subsequent 4 weeks will be with TBT intervention for 20 minutes.
 - b. Of the 8 weeks of PR, first 4 weeks will be with TBT intervention for 20 minutes, then next 4 weeks will be of sessions of normal breathing exercises for 20 minutes.
- 2) Comparing MDVE to normal breathing:
 - a. Of the 8 weeks of PR, first 4 weeks will be sessions of normal breathing exercises for 20 minutes, then subsequent 4 weeks will be with WT intervention for 20 minutes.
 - b. Of the 8 weeks of PR, first 4 weeks will be with MDVE intervention for 20 minutes, then next 4 weeks will be of sessions of normal breathing exercises for 20 minutes.

These interventions would be performed after usual PR time, when patients would be normally discharged home. Therefore, no additional monitoring is expected.

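### Section 2.0 separates a comparison with no intervention (Aim 1) from one with normal breathing (Aim 2), but the four arms offer only the second; hypothesis (c) is worded as a non-significant result

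*Protocol*

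**What the plan says.** Protocol Section 2.0 sets three aims with the same outcomes (Borg dyspnea score, FEV1, FVC, NIF, peak flow). Aim 1 asks whether the exercises improve these "in patients referred for PR, compared to no intervention". Aim 2 asks whether they "improve subjective pulmonary symptoms and objective pulmonary function, compared to calm normal breathing". Aim 3 asks whether the two techniques differ. Hypothesis (c), which follows the aims, predicts that TBT and MDVE will not differ significantly. It gives no margin.

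Section 6.0 fixes the design: "we propose 16 participants in total, 4 in each arm of the study". Each arm joins a four-week normal-breathing period to a four-week technique period. In arm 1a, for example, the "first 4 weeks will be sessions of normal breathing exercises for 20 minutes, then subsequent 4 weeks will be with TBT intervention". The summary later in Section 6.0 lists "20-minute sessions after PR for intervention (TBT or MDVE) or normal breathing for twice a week for the 8 weeks", and Section 9.0 describes weeks 1 to 8 as PR "with phonation intervention (TBT or MDVE) or silent breathing time".

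Section 17.0 says that no power analysis will be done and that the tests are not expected to reach significance at this sample size.

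**The concern.** Two aims with the same exercises and outcomes can differ only in their comparator. A reader who sees them listed separately expects the design to hold two comparators, and it appears to hold one. The report could then present a single contrast as the answer to two questions. It could also present improvement during PR as an effect relative to no intervention, although every participant is receiving PR at the time.

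Hypothesis (c) raises a related difficulty. A small trial will usually return a non-significant result whether or not the techniques differ. A hypothesis worded as non-significance is therefore likely to look confirmed for a reason unrelated to the techniques. Section 3.0 makes comparing the two techniques an objective and intends a larger study of the same question, so how this result is expressed will carry forward.

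**Working it through.** **Step 1: which comparators exist.** From Section 6.0, arm by arm:

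| Arm | Weeks 1–4 | Weeks 5–8 |
|---|---|---|
| 1a | normal breathing | TBT |
| 1b | TBT | normal breathing |
| 2a | normal breathing | MDVE |
| 2b | MDVE | normal breathing |

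Arm 2a actually reads "then subsequent 4 weeks will be with WT intervention for 20 minutes". It is taken here as MDVE because it stands under the MDVE comparison and no third technique is described. It has a normal-breathing period either way, so the conclusion on Aim 1 does not depend on this reading.

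Count: 4 arms × 2 periods = 8 arm-periods, of which 4 are technique (2 TBT, 2 MDVE), 4 are normal breathing and 0 are PR alone. Section 6.0 schedules PR three times a week and the added sessions twice a week, so one PR visit a week may have no added session. That would apply in every arm and period, so it supplies no contrast. No external or historical PR-alone group is described.

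**Step 2: what Aim 1 can mean.**

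- *No intervention means the normal-breathing period.* Section 1.0 lists only TBT and MDVE as research interventions, and Sections 6.0 and 9.0 set intervention (TBT or MDVE) against normal or silent breathing. On that usage, Aim 1 has the same comparator as Aim 2 and repeats it.
- *No intervention means PR alone.* No randomised comparator exists. What remains is change from baseline, using the baseline, week 4 and week 8 measurements. All participants undergo PR between those points, so such a change mixes the technique with PR.

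**Step 3: hypothesis (c).** The protocol's own figure first: 4 arms × 4 participants = 16, which agrees with the stated total. Two arms contain each technique, so the TBT–MDVE comparison has 2 × 4 = 8 per technique.

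The protocol states no significance level, SD or effect size. As an illustration, assume a simple two-sample t-test, two-sided 5%, with differences expressed in units of the SD of whichever outcome is analysed:

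- Degrees of freedom: 8 + 8 − 2 = 14.
- Standard error: √(1/8 + 1/8) = 0.50 SD.
- 95% CI half-width: t(0.975, 14) × 0.50 = 2.145 × 0.50 = 1.07 SD.
- Noncentrality: true difference ÷ 0.50. Power comes from the noncentral t distribution with 14 df.

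| True difference | Noncentrality | Power | Non-significant |
|---|---|---|---|
| 0.5 SD | 1.0 | 0.154 | about 85% |
| 0.8 SD | 1.6 | 0.320 | 68% |
| 1.0 SD | 2.0 | 0.461 | 54% |

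Even if the techniques truly differ by a full SD, the outcome that (c) predicts would occur more often than not.

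**The case against.** The strongest reply on Aim 1 is that the protocol largely settles its own meaning. It uses the word intervention only for TBT and MDVE, and Section 3.0 gives just two objectives: whether the exercises work, and how the two techniques compare. Aim 1 is then redundant wording. An analysis plan could map it to the normal-breathing periods, or to a change from baseline labelled as uncontrolled. This stands. A reader might infer that a third of the trial's aims is unanswerable or that the trial lacks a control. The documents do not support that, because there is a randomised control, normal breathing, and it serves Aim 2. What an analysis plan cannot do is create a PR-alone period, so the separate listing still promises more than the arms contain.

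On hypothesis (c), the reply is that it states an expectation and not a decision rule, that Aim 3 is neutrally worded, and that Section 17.0 already warns about the sample size. This also stands. A reader might infer that the investigators will declare the techniques similar after a non-significant test, but the protocol nowhere says so. The remaining weakness is that the hypothesis is expressed as a test result that is likely under both similarity and difference.

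The power figures come from a simplified comparison. Section 17.0 names chi-squared tests and ANOVA across four categories, and each participant also has a normal-breathing period that could be used within person. The figures therefore show the order of magnitude only.

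**Conclusion.** The point holds and is minor for a pilot. Aim 1 has no randomised comparison of its own: none of the 8 arm-periods is PR alone. The more natural reading is that it duplicates Aim 2. The alternative is an uncontrolled change confounded with PR. This conclusion follows from the protocol's text and needs no assumption.

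Hypothesis (c) is secondary. A non-significant result could not support it at this size. With the nominal 8 per technique, a simple t-test and an assumed two-sided 5% level, about 85% of such trials would be non-significant at a true difference of 0.5 SD, and the 95% CI would extend about 1.07 SD either side of the estimate. The effect sizes are assumptions, since the protocol gives none. The practical effect is limited because the protocol claims no power, expects no significant findings, and plans a larger study to compare the techniques.

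**What to change.** In Section 2.0:

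- Merge Aim 1 into Aim 2, worded as technique sessions versus normal-breathing sessions during PR, or delete Aim 1. Report no result as a randomised comparison with no intervention. If change from baseline is described, label it as uncontrolled.
- Restate hypothesis (c) along these lines: *the TBT–MDVE difference will be estimated with a 95% confidence interval, and a non-significant result will not be read as showing that the techniques are similar.*

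The cost is a rewording of one section. Arms, visits and sample size do not change. The downside is that two stated claims become weaker, but the present design cannot support either of them.
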